6.2.9.6 Bleeding and Spotting

Vaginal bleeding and spotting will be recorded daily by subjects in e-diary. The total number of bleeding or spotting days will be summarized for each cycle in safety and ECYC population. The missing value imputation at cycles will be calculated similarly as the above Section 6.2.9.4.

In addition, bleeding and spotting will be summarized separately (i.e. none, spotting, light bleeding, medium bleeding, heavy bleeding). Subjects who discontinue the study due to bleeding complaints prior to completing one 28-day cycle will be included in the bleeding analysis.

When bleeding occurred, flows heavier than when not using hormones will also be summarized by cycle.

All bleed and spotting e-diary data will be presented in data listings.

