4.1 Efficacy Variable

The primary outcome measure is effectiveness and will be evaluated as absence of pregnancy during study device use.

E-Diary data from the day of study placement to end of study/exit will collect the following information:

- 1) Menstrual and intermenstrual bleeding;
- 2) Vaginal intercourse;
- 3) Pain with intercourse;
- 4) Use of additional contraception;
- 5) Menstrual pain or cramping;
- 6) LevoCept expulsion

When data is still missing for a day after final attempt to have subject complete E-Diary, Vaginal intercourse, Pain with intercourse and Use of additional contraception will be collected for that specific missing day during monthly contact. The CRF collected data is used as a back-up. It is always preferred for the subject to complete the E-Diary data. If it occurs for a particular day that there is both subject data and CRF collected data, the subject data will take precedence and be used.

1. Pearl index

The primary efficacy variable is Pearl index. The Pearl index based on 28-day cycles and defined as the number of pregnancies per 100 woman-years (with one year comprising 13 28-day cycles). It will be calculated as:

$$\text{Pearl index} = \frac{N \times 1300}{L} = \frac{\text{Number of pregnancies} \times 1300}{\text{Number of woman-cycles of pregnancy at risk}}$$

Where n is the number of pregnancies, L is the number of woman-cycles of pregnancy at risk.

Only pregnancies judged to have occurred during study device use, or for which the estimated date of conception was within 7 days after study device removal or calculated date of expulsion are counted.

The number of woman-cycles of pregnancy at risk is the sum of the number of 28-day cycles for each subjects from the date of study device successful placement through the date of study device removal/expulsion or pregnancy, whichever comes earlier, excluding the following (unless the subject became pregnant in the cycle):

- Cycles where back-up contraception or emergency contraception use was reported by the subject;

- Cycles with no intercourse.

The cycle is defined as 28 days with the day of study device successful placement as cycle 1 day 1. The last cycle of pregnancy risk can be a partial cycle and the number of cycles can have one decimal place. The number of cycles (NC) of pregnancy risk for each subject will be calculated as:

$$NC = \frac{\min(\text{Date of removal/expulsion, Date of conception}) - \text{Date of placement}}{28}$$

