5.6 Evaluable for Cycle Control Analysis Population

Evaluable for Cycle Control (ECYC) analysis population will include only those safety subjects with at least one cycle for which: A) a pregnancy did not occur; and B) there is bleeding related e-diary data.

6 Analysis Methods

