6.2.9.4 Device Subject Discomfort

Experience of any menstrual pain or cramping will be recorded daily by the subject in the e-diary. The occurrence and severity of discomfort will be summarized for each cycle in safety and ECYC population. The summary will present the number of days, the worst pain grade and the highest frequency occurrence pain grade in each cycle with menstrual pain or cramping.

If a cycle has less than 28 days but at least 14 days data, missing value will be imputed by the average in the same cycle for the subject, and then rounded to nearest integer.

For example, a subject at Cycle 6 has only 20 days data, of which 3 days with "Cramping". Total number of "Cramping" days at this cycle for her will be estimated as:

$$3 + (3 / 20 \times (28 - 20)),$$

which will be 4 after rounding.

If a cycle has less than 14 days data, no imputation for missing value, number of days for this cycle would be treated as missing.

All device subject discomfort e-diary data will be presented in data listings.

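### SAP 6.2.9.6 says women who exit early for bleeding are included in the bleeding analysis, but its missing-data rule leaves those with fewer than 14 diary days without a cycle 1 count

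*SAP*

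**What the plan says.** SAP 6.2.9.6 summarises bleeding and spotting days for each cycle, in the safety and ECYC populations. On early exits it states: "Subjects who discontinue the study due to bleeding complaints prior to completing one 28-day cycle will be included in the bleeding analysis". Protocol 20.7 (Bleeding and Spotting Patterns) makes the same commitment and sets no minimum number of diary days.

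On incomplete diaries, 6.2.9.6 refers back to the section on menstrual pain: "The missing value imputation at cycles will be calculated similarly as the above Section 6.2.9.4". That section has two branches:

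- 14 to 27 days: "If a cycle has less than 28 days but at least 14 days data, missing value will be imputed by the average" of the same woman's cycle, then rounded.
- Fewer than 14 days: "If a cycle has less than 14 days data, no imputation for missing value, number of days for this cycle would be treated as missing".

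No exception is written for women who leave because of bleeding. SAP 8.2, which lists changes from the protocol's planned analyses, does not mention the 14-day minimum.

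**The concern.** For one group of women the two instructions in 6.2.9.6 cannot both be followed. A woman who leaves for bleeding with fewer than 14 days of bleeding data is to be included, yet the only value she could contribute is set to missing. A programmer would have to choose, and the rule as written leads to leaving her out.

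The missing value is not incidental: she has too few days because she left, and she left because of the outcome being summarised. Bleeding and spotting patterns are a named tolerability measure (protocol 5.2). If such women bleed more than those who stay, which is plausible given why they left, the cycle 1 summary understates bleeding in the device's favour.

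**Working it through.** **Step 1. Reproduce the SAP's example.** With *b* symptom days among *d* diary days, the rule in 6.2.9.4 gives *b* + (*b*/*d*) × (28 − *d*), rounded, for 14 ≤ *d* < 28, and missing for *d* < 14. The SAP's example has *d* = 20 and *b* = 3: 3 + (3/20) × 8 = 4.2, which rounds to 4. This agrees with the SAP.

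**Step 2. Apply the rule to a woman who bleeds on every recorded day (*b* = *d*).**

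| Diary days *d* | Calculation | Cycle 1 count |
|---|---|---|
| 1 to 13 | none | missing |
| 14 | 14 + (14/14) × 14 | 28 |
| 20 | 20 + (20/20) × 8 | 28 |
| 27 | 27 + (27/27) × 1 | 28 |

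Of the 27 possible incomplete lengths, 13 give a missing count and 14 give a retained, scaled count. The contradiction is therefore confined to women with fewer than 14 days of data.

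**Step 3. Does another value stand in for the missing one?**

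- *Another cycle:* no. SAP 4.1 says: "The cycle is defined as 28 days with the day of study device successful placement as cycle 1 day 1". A woman who leaves before finishing it has no second cycle.
- *Back-up data:* no. For missed diary days SAP 4.1 says: "Vaginal intercourse, Pain with intercourse and Use of additional contraception will be collected for that specific missing day during monthly contact". Bleeding is not named, so diary gaps can also bring a woman who left after day 14 below the threshold.
- *Population membership:* she is in the safety population by virtue of successful placement (SAP 5.3). ECYC asks for a cycle without pregnancy for which "there is bleeding related e-diary data", with no minimum number of days. She therefore counts in the header N of Table 14.3.6.1.1 but not in n, mean, SD, median, minimum or maximum. The shell has no row or footnote that would show this.

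**Step 4. Possible size.** Suppose *k* such women would each have a count of 28 and the remaining women average *m* days. Among 250 women, leaving the *k* out lowers the cycle 1 mean by *k* × (28 − *m*)/250. The 250 is the protocol's planned maximum number of placements, taken here as all successful and all contributing to cycle 1. The values of *k* and *m*, and daily bleeding in these women, are assumptions that the documents do not supply.

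| *k* | *m* = 10 | *m* = 12 | *m* = 15 |
|---|---|---|---|
| 1 | 18/250 = 0.07 | 16/250 = 0.06 | 13/250 = 0.05 |
| 5 | 90/250 = 0.36 | 80/250 = 0.32 | 65/250 = 0.26 |
| 10 | 180/250 = 0.72 | 160/250 = 0.64 | 130/250 = 0.52 |

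The value 28 is used only to gauge size. The shift shrinks if these women bled on fewer of their recorded days, and it vanishes if their rate equals that of the others.

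**The case against.** The strongest reply is that there is no contradiction. The rule is to be applied similarly, not identically, and the inclusion sentence comes later and is more specific, so it could be read as an exception. It could also be read as a population rule: the protocol synopsis and SAP 5.6 both ask for at least one cycle, and the sentence may only make clear that an unfinished first cycle does not disqualify a woman.

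Neither reading settles the matter. If an exception is meant, it is not written, and nothing says what value she would receive. If only membership is meant, the sentence adds nothing for the safety population, to which she already belongs, and she still has no day count in either table.

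A second reply is that these women are visible elsewhere. Discontinuation is summarised, adverse events leading to removal or exit have their own tables, the adverse event listing has a column for relation to bleeding, and "All bleed and spotting e-diary data will be presented in data listings". This stands as far as it goes: the exits are not hidden. None of these outputs summarises bleeding days, however. It is also true that SAP 6.2.9 plans descriptive safety summaries only, so no test depends on this.

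A third reply concerns the remedy, and it stands. Scaling 1 to 13 days up to 28 would be unsound. Protocol 4.1.2 places insertion within the first 7 days of the menstrual cycle for women not using hormonal contraception, so their first diary days may be menses. Three such days, all with bleeding, would become 3 + (3/3) × 25 = 28. Possible understatement would be exchanged for built-in overstatement.

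**Conclusion.** The point holds for women who discontinue for bleeding complaints with fewer than 14 days of bleeding diary data. For them SAP 6.2.9.6 contradicts itself and, as written, leaves the commitment in protocol 20.7 without effect on the day counts.

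A reader might infer that every woman who leaves for bleeding before finishing a cycle is dropped. That is not so: those with 14 to 27 days are kept and scaled. A reader might also infer that the worst early bleeding, or the top of the distribution, is removed. The documents do not support that either. They give no number, timing or severity of such exits, and women who bleed daily and leave on days 14 to 27 with complete diaries, or who stay, are counted at 28.

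Cycle 1 bleeding may therefore be understated, by an unknown amount. On the assumptions in Step 4 the shift is about 0.06 days on the mean per such woman (0.05 to 0.07 for *m* from 15 down to 10). The effect on the mean is likely to be modest unless there are several such women. The case for a change rests on the contradiction, on missingness that follows from the outcome, and on the low cost of correction.

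**What to change.** In SAP 6.2.9.6 and Table 14.3.6.1.1 (and its ECYC counterpart):

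1. State that women who discontinue for bleeding complaints with fewer than 14 days of bleeding data are not dropped, and give their number.
2. Report their observed bleeding and spotting days over their observed device days, unscaled, in a separate row.
3. Show the cycle 1 summary as a proportion of observed device days, with and without these women. This puts all women on one scale and avoids filling days after exit with the pre-exit rate.
4. Say how a bleeding exit is identified, since the exit reasons in SAP 4.2 have no bleeding category. The bleeding column in Listing 16.2.7.1 and the specified text in Listing 16.2.1.1 are available for this.

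The cost is SAP wording, an extra row and a second version of the cycle 1 summary, with no new data collection. The downside is that proportions from a few women with few days are noisy, which the separate row makes plain.

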6.2.9.7 Device Expulsion and Removal

Device expulsion will be recorded daily by the subject in e-diary. Device removal procedure will be recorded in the CRF. Cumulative study device removal rates and expulsion rates will be summarized at 1-year (study day 1 - 364), 2-year (study day 365 - 728), and 3-year (study day 729 +).

6.2.9.8 Vital Signs

Vital signs (temperature, heart rate, respiration, blood pressure), weight and BMI will be summarized using descriptive statistics at baseline and at each post-baseline time point. Changes from baseline will also be summarized by visit for heart rate, blood pressure, weight and BMI.

Vital signs, weight and BMI will be included in data listings.

6.2.9.9 Physical Examination

Physical examination results will be included in data listings only.

7 Interim Analyses

Interim analyses are planned for this study when all subjects have completed one year of treatment. The analyses for the interim CSR is the same as the planned analyses for the final CSR.

8 Changes in the Conduct of the Study or Planned Analysis

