## 2. STUDY DURATION

Subject enrollment will take approximately 5 months. Each subject will be followed for 12 months after device placement for the protocol endpoints, and then every 6 months thereafter for up to 24 additional months for those subjects who wish to continue study device use.

---

Alan Guttmacher Institute Fact Sheets Oct 2013 ([www.guttmacher.org](http://www.guttmacher.org)): <https://www.guttmacher.org/fact-sheet/contraceptive-use-united-states#1>

[Changes in Use of Long-Acting Reversible Contraceptive Methods Among U.S. Women, 2009-2012.](#) Kavanaugh ML, Jerman J, Finer LB.

Obstet Gynecol. 2015 Nov;126(5):917-27. doi: 10.1097/AOG.0000000000001094. PMID: 26444110

accessed August 11, 2014.

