#### **12.4 Long-term Follow-up, post 52-weeks visit (Every 6 Months: Months 18-30 ( $\pm 4$ wks) and 3 yrs ( $-3$ wks/ $+4$ wks))**

At 52 weeks, subjects will be allowed to continue with the study device with a follow-up office visit every 6 months for a maximum of three years post study device placement. During these visits, the following will be performed:

- Vital signs and weight
- Pelvic exam (string check)
- Transvaginal ultrasound If unable to confirm IUD placement by string check or if indicated
- Pregnancy test, urine
- Interval and concurrent medications
- Adverse events
- Concomitant contraception
- Need for contraception (If a subject believes the study device may have been expelled or is no longer in place, the subject should call for an urgent study visit and refrain from having sex or use appropriate non-hormonal contraception until further evaluation is completed. (See Section 4.7 for details)
- Verify sexual activity and any back-up method is documented
- Instruct the subject to contact the site immediately if she thinks she has become pregnant.

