## **20.6 Primary Outcome**

The primary outcome measure is effectiveness and will be evaluated as absence of pregnancy during LevoCept use. Pregnancies judged to have occurred while a study device was in place (determined by ultrasound and medical assessments) will be included in the analysis of pregnancies.

For the primary evaluation of effectiveness, the Pearl index (and 95% confidence intervals) will be calculated in subjects aged 18-35 at the time of LevoCept placement through the date of LevoCept removal or pregnancy, excluding the following (unless the subject became pregnant in the cycle):

- Cycles where back-up contraception use was reported by the patient
- Cycles with no intercourse.
- Cycles in which emergency contraception was used

The Pearl Index is based on 28-day cycles and defined as the number of pregnancies per 100 woman-years (with one year comprising 13 28-day cycles). The cycle is defined as 28 days with the day of LevoCept placement as cycle 1

day 1. Pearl index will be summarized annually for each of the 3 years and cumulatively.

The EP population will be used for the primary evaluation of effectiveness.

Life table (Kaplan-Meier method) analyses will be used as further assessment of pregnancies. Pregnancy rate will also be summarized annually for each of the 3 years and cumulatively.

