14.1.11.3 Both Prior and Concomitant Medication (All Enrolled Subjects)

Update the cell at first column first row to 'Patients with both prior and Concomitant Medications'.

CONFIDENTIAL

Sebela Pharmaceuticals Development LLC
CMDOC-0022

Page x of y

Table 14.2.1
Pearl Index (EP Population)

	Number of Subjects	Number of Pregnancies	Number of Woman-Cycles at Risk	Pearl Index	95% CI for Pearl Index
1-Year					
All EP Subjects	n	n	n	x.xx	x.xx, x.xx
EP Subjects by Parity					
Parous	n	n	n	x.xx	x.xx, x.xx
Nulliparous	n	n	n	x.xx	x.xx, x.xx
EP Subjects by BMI					
Underweight (<18.5)	n	n	n	x.xx	x.xx, x.xx
Normal (18.5-24.9)	n	n	n	x.xx	x.xx, x.xx
Overweight (25.0-29.9)	n	n	n	x.xx	x.xx, x.xx
Obese (>=30)	n	n	n	x.xx	x.xx, x.xx
2-Year					
All EP Subjects	n	n	n	x.xx	x.xx, x.xx
EP Subjects by Parity					
Parous	n	n	n	x.xx	x.xx, x.xx
Nulliparous	n	n	n	x.xx	x.xx, x.xx
EP Subjects by BMI					
Underweight (<18.5)	n	n	n	x.xx	x.xx, x.xx
Normal (18.5-24.9)	n	n	n	x.xx	x.xx, x.xx
Overweight (25.0-29.9)	n	n	n	x.xx	x.xx, x.xx
Obese (>=30)	n	n	n	x.xx	x.xx, x.xx
Cumulative 2-Year					
.....					
3-Year					
.....					
Cumulative					

EP=Evaluable for Pregnancy.

Reference: Listing xxx.

Program Location: \\xx\xxx\xxx\xxx\xxxxxx\xxxxxxxxxxxxxxxxxxxx\xxxx\xxxxx.sas

date

time

Programmer note:

1.Table will continue with for Cumulative 2-Year, 3-Year,Cumulative

CONFIDENTIAL

Sebela Pharmaceuticals Development LLC
CMDOC-0022

Page x of y

Table 14.2.2
Pregnancy Rate (EP Population)

	Parous (N=xx)	Nulliparous (N=xx)	All Subjects (N=xx)
Number of Subjects with Pregnancy	n (%)	n (%)	n (%)
Number of subjects who was not Pregnant(Censored)	n (%)	n (%)	n (%)
Pregnancy Free (Days)			
Pregnancy Rate[1]			
1-Year	xx	xx	xx
2-Year	xx	xx	xx
Cumulative 2-Year	xx	xx	xx
3-Year	xx	xx	xx
Cumulative	xx	xx	xx
Range (Subjectswith Pregnancy)	xx -xx	xx -xx	xx -xx
Range (All Subjects)	xx -xx	xx -xx	xx -xx

[1] Kaplan-Meier product-limit estimates.

Reference: Listing xxx.

Program Location: \\xx\xxx\xxx\xxx\xxxxxx\xxxxxxxxxxxxxxxx\xxxx\xxxxx.sas

date

time

CONFIDENTIAL

Sebela Pharmaceuticals Development LLC
CMDOC-0022

Page x of y

Table 14.3.1.1.1
Overall Summary of Treatment-Emergent Adverse Events (Safety Population)

	Events (N=xx) n	Subjects (N=xx) n (%)
Onset Time Frame:		
Missing	n	n (%)
From Day 1 through Day 42(Week 6)	n	n (%)
From Day 43 through Day 91(Week 13)	n	n (%)
From Day 92 through Day 182(Week 26)	n	n (%)
From Day 183 through Day 364(Week 52)	n	n (%)

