Some Pain	n (%)
Painful	n (%)
Moderately Painful	n (%)
Very Painful	n (%)
Medication given during the procedure	
n	n
Yes	n (%)
No	n (%)
Mechanical Dilatation	
n	n
Yes	n (%)
No	n (%)

Note: Percentages are based on the number of subjects specified in the column header, i.e. N, unless small n is specified for each category.

Reference: Listing xxx.

Program Location: \\xx\xxx\xxx\xxx\xxxxxx\xxxxxxxxxxxxxxxx\xxxx\xxxxx.sas

date

time

CONFIDENTIAL

Sebela Pharmaceuticals Development LLC
CMDOC-0022

Page x of y

Table 14.3.5.3
Device Expulsion/Removal and Subject Pain During the Procedure (Safety Population)

Description	All Subjects (N=xx) n (%)
Cumulative 1-Year Device Expulsion Rate	n (%)
Cumulative 1-Year Device Removal Rate	n (%)
Cumulative 2-Year Device Expulsion Rate	n (%)
Cumulative 2-Year Device Removal Rate	n (%)
Cumulative 3-Year Device Expulsion Rate	n (%)
Cumulative 3-Year Device Removal Rate	n (%)
Device Expel Prior to This Visit	
n	n
Yes	n (%)
No	n (%)
If Yes, Expulsion Status	
n	n
Complete	n (%)
Partial	n (%)
Was removal accomplished by pulling the strings Without Difficulty	
n	n
Yes	n (%)
No	n (%)
If No, Select All That Apply:	
n	n (%)
Required significant force to pull out with strings	n (%)
Required use of ultrasound guidance	n (%)
Required use of Alligator forceps	n (%)
Required use of IUD hook	n (%)
Required use of other instrument	n (%)
Unable to remove in office initially, required second office visit for successful removal	n (%)
Unable to remove in office - removed in OR	n (%)
Other	n (%)

Note: Percentages are based on the number of subjects specified in the column header, i.e. N, unless small n is specified for each category.
Reference: Listing xxx.

Program Location: \\xx\xxx\xxx\xxxxxx\xxxxxxxxxxxxxxxx\xxxx\xxxxx.sas

date

time

CONFIDENTIAL

Sebela Pharmaceuticals Development LLC
CMDOC-0022

Page x of y

Table 14.3.5.3
Device Expulsion/Removal and Subject Pain During the Procedure (Safety Population)

Programmers note: Continued table

Description	All Subjects (N=xx) n (%)
Ease of Device Removal	
n	n
Very Easy	n (%)
Easy	n (%)
Neither Easy nor Difficult	n (%)
Difficult	n (%)
Very Difficult	n (%)
Device Removal Pain	
n	n
No Pain	n (%)
Some Pain	n (%)
Painful	n (%)
Moderately Painful	n (%)
Very Painful	n (%)
Medication Given During the Procedure	
n	n
Yes	n (%)
No	n (%)

Note: Percentages are based on the number of subjects specified in the column header, i.e. N, unless small n is specified for each category.

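### The one-year interim CSR repeats every final analysis, so 2-Year, 3-Year and cumulative rows would be printed with Year 2 barely begun and Year 3 empty

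*SAP*

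**What the plan says.** SAP Section 7 has two sentences. The first gives the trigger: "Interim analyses are planned for this study when all subjects have completed one year of treatment". The second gives the content: "The analyses for the interim CSR is the same as the planned analyses for the final CSR".

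The final set of analyses reaches well past one year:

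- **Pearl Index.** Protocol 20.6: "Pearl index will be summarized annually for each of the 3 years and cumulatively". The layout of SAP Table 14.2.1 opens with the 1-Year and 2-Year blocks, and its programmer note adds the rest: "Table will continue with for Cumulative 2-Year, 3-Year,Cumulative".
- **Pregnancy rate.** Table 14.2.2 has the same periods as Kaplan-Meier estimates. Figures 14.2.1.1 and 14.2.1.3 plot the whole follow-up and the first two years.
- **Expulsion and removal.** Table 14.3.5.3 has 1-, 2- and 3-year rows, the last set including "Cumulative 3-Year Device Expulsion Rate". Its footnote bases percentages on the column N. SAP 4.2 likewise divides by subjects enrolled by the time-point, not by subjects followed to it.
- **Adverse events.** Table 14.3.1.13 has a column for onset after 12 months.

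On timing, Protocol Section 2 says: "Subject enrollment will take approximately 5 months". Follow-up after the first 12 months is "every 6 months thereafter for up to 24 additional months for those subjects who wish to continue study device use". After Week 52, the 28-day contacts in Protocol 12.4.1 cover sexual activity and back-up contraception. The next scheduled urine pregnancy test for a woman who keeps the device is at the Month 18 visit.

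**The concern.** The interim is timed for the 12-month protocol endpoints, and the study's purpose is to support starting Phase III. If Section 7 is followed literally, the same report also prints results labelled 2-Year, 3-Year and Cumulative.

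The crude expulsion and removal percentages have no mechanism for incomplete follow-up. A woman seen for only part of Year 2 counts in the 2-year and 3-year denominators as if she had been followed throughout. A reader would see long-term rates hardly above the 1-year rate and could take this as evidence of good retention.

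For the Pearl Index, early Year-2 cycles would enter the denominator with little scheduled pregnancy testing behind them. There is also a practical gap. SAP 4.1 ends time at risk at removal, expulsion or conception. A woman still using the device at the interim has none of these dates, so the formula cannot be applied to her without a cut-off date.

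**Working it through.** **Inputs.** Accrual about 5 months (Protocol 2). Trigger: all subjects at one year (SAP 7). Year 2 begins on day 365 and Year 3 on day 729 (SAP Table 2). Week 52 visit window, days 351 to 385 (SAP Table 1). Earliest Month 18 visit: day 533 in SAP Table 1, or day 547 − 28 = 519 under the 4-week window in Protocol 12.4. Planned: 225 women aged 18-35, 2,015 evaluable cycles, 1 pregnancy, 9.2% of cycles lost to no intercourse or back-up use (Protocol, Sample Size).

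**The plan's own figures.** 13 × 28 + 1 = 365 and 26 × 28 + 1 = 729 match SAP Table 2. The Pearl Index of 1 × 1300/2015 = 0.645 matches the stated 0.6.

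**Follow-up at the trigger.** Accrual is 5 × 365.25/12 = 152.2 days. Uniform accrual is assumed.

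| Last woman at day | First woman at day | Cycles into Year 2, first woman | Share past day 519 | Share past day 533 |
|---|---|---|---|---|
| 364 | 516 | 5.4 | 0% | 0% |
| 379 | 531 | 6.0 | 8% | 0% |
| 385 | 537 | 6.2 | 12% | 3% |

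Shares are by placement date, for example (537.2 − 519)/152.2 = 12%. Every continuing woman has reached the Year 2 boundary, and nobody is near day 728.

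**Share of Year 2 seen.** With the cut on the last woman's day 364, the mean per continuing woman is 152.2/2 = 76 days, or 2.7 of 13 cycles (21%). At day 385 it is (76.1 + 21)/28 = 3.5 cycles (27%). So 73 to 79% of Year 2 and all of Year 3 is unobserved.

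**Expulsion and removal.** With no follow-up past about day 537, no event can fall in Year 3, so the 3-year cumulative count equals the 2-year count. Both equal the 1-year count plus whatever occurred in that first fifth to quarter of Year 2, over an unchanged N.

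**Kaplan-Meier.** Nobody is at risk beyond about day 537, so an estimate at 2 or 3 years is the last value carried forward.

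**Pearl Index.** The documents give no continuation rate, so 40 to 80% is assumed. As a middle case, an average of 10 of 13 cycles under constant dropout solves (1 − e^(−13h))/h = 10, giving h = 0.0423 and 57.7% still in use at cycle 13.

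Year-2 cycles = 225 × continuation × (76.1/28) × 0.908:

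| Continuing | Year-2 cycles | Upper 95% limit at 0 pregnancies (3.689 × 1300/cycles) | Cumulative index with 1 pregnancy | Fall from 0.645 |
|---|---|---|---|---|
| 40% | 222 | 21.6 | 0.581 | 10% |
| 57.7% | 320 | 15.0 | 0.557 | 14% |
| 80% | 444 | 10.8 | 0.529 | 18% |

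The cumulative index is 1300/(2015 + cycles). The fall is a ceiling: it applies only if no Year-2 pregnancy has yet been found. A later cut adds cycles. At day 385 the same formula gives 283 to 567 cycles and a largest fall of 283/2298 = 12% to 567/2582 = 22%.

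**The case against.** The strongest reply is that the result that matters is untouched. Table 14.2.1 has its own 1-Year row, cycles 1 to 13 are fixed to days 1 to 364, and there is a Kaplan-Meier figure to one year and a first-year adverse event table (14.3.1.12). No test or stopping rule depends on the interim. This stands. A reader might infer that the 12-month Pearl Index is diluted; it is not.

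A reader might also infer that no woman has reached Year 2, or that its cycles are wholly untested. The documents do not support either. The trigger puts every continuing woman in Year 2. Women are told to contact the site at once if they suspect pregnancy, a Week 52 test can fall after day 364, and exits have a home test at 17 days or, after expulsion, at 6 to 8 weeks. The share reaching the Month 18 test also depends on accrual, on the cut date and on which window applies. With 6 months' accrual, 16 to 27% would be past day 519. With 5 months and data frozen 30 to 60 days after the last woman's day 364, it would be about 18 to 38%.

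Nor would a zero in the 2-Year row show missed pregnancies. At the plan's own rate, 222 to 444 cycles carry 0.11 to 0.22 expected pregnancies (cycles × 0.645/1300), so zero is 80 to 90% likely even with perfect detection. The largest fall in the cumulative index is small beside the planned interval of 0.1 to 3.3.

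Two further replies carry part of their weight. The column-N denominator applies at the final analysis too, but at the interim incomplete follow-up affects every continuing woman. And SAP Sections 6.2.7 and 6.2.8 are not in the text available here, so a cut-off stated there cannot be ruled out.

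**Conclusion.** The point holds for the later-year and cumulative rows only. As written, Section 7 calls for results at horizons that nobody will have completed. The clearest harm is in Table 14.3.5.3, where roughly the 1-year expulsion and removal rates would appear under 2-year and 3-year labels. The Kaplan-Meier 2- and 3-year values would be carried forward with no one at risk. The 2-Year Pearl Index would be very imprecise, and the cumulative index could be lowered modestly.

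The absence of any completed Year 2 is robust: 6 months' accrual with the last woman at day 385 puts the first woman only at about day 568. The Month 18 share (about 0 to 12% at the trigger) and the cycle counts are less firm. They rest on uniform 5-month accrual, a cut between the last woman's days 364 and 385, and, for the cycle counts, an assumed continuation of 40 to 80%. This is worth changing before the interim lock, but it does not threaten the 12-month primary result.

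**What to change.** Replace the second sentence of SAP Section 7 with a stated data cut-off and a Year-1 limit:

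- Efficacy, bleeding and pain summaries use cycles 1 to 13. Expulsion, removal and adverse event summaries use data through day 364 or the Week 52 visit; choose one and state it.
- The 2-Year, Cumulative 2-Year, 3-Year and Cumulative rows of Tables 14.2.1 and 14.2.2, the 2- and 3-year rows of Table 14.3.5.3, the columns beyond 12 months, and Figures 14.2.1.1 and 14.2.1.3 are not produced at the interim. They follow once all continuing subjects have completed the corresponding Week 104 or Week 156 visit or have exited.
- The cut-off is set so that the already scheduled 17-day post-removal test, or the 6-8-week post-expulsion test, has been completed or recorded as missed for Year-1 exits. SAP 4.1 counts conceptions up to 7 days after removal or expulsion. Women placed in the last 17 days of accrual (17/152.2 = 11%) who exit at Week 52 could not have had the removal test when the last woman reaches one year.

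The two Month 18 windows (2 weeks in Protocol Table 1 and the SAP, 4 weeks in Protocol 12.4) also need to be reconciled.

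The cost is wording and an analysis-flag filter. Early Year-2 data wait for a later report, though serious adverse events can stay in the listings, and the interim lock may come a few weeks later.
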